**Table 2. Time Point Response: Patients with Nontarget Disease Only**

Nontarget Lesions	New Lesions	Overall Response
CR	No	CR
Non-CR/non-PD	No	Non-CR/non-PD a
Not all evaluated	No	NE
Unequivocal PD	Yes or No	PD
Any	Yes	PD

Abbreviations: CR = complete response; PD = progressive disease ; NE = inevaluable.

a non-CR/non-PD is preferred over SD for nontarget disease.

### Frequency of Tumor Re-Evaluation

A baseline tumor evaluation must be performed within 4 weeks before patient begins study treatment. Frequency of tumor re-evaluation while on and adapted to treatment should be protocol-specific and adapted to the type and schedule of treatment. In the context of Phase 2 studies where the beneficial effect therapy is not known, follow-up every 6-8 weeks is reasonable. Normally, all target and non-target sites are evaluated at each assessment using the same method. However, bone scans may need to be repeated only when CR is identified in target disease or when progression in bone is suspected.

### Confirmatory Measurement/Duration of Response

#### *Confirmation:*

The main goal of confirmation of objective response in clinical trials is to avoid overestimating the response rate observed. The confirmation of response is particularly important in *nonrandomized trials* where response (CR/PR) is the primary end point. In this setting, to be assigned a status of PR/CR, changes in tumor measurements must be confirmed by repeat assessments that should be performed no less than 4 weeks after the criteria for response are first met. To confirm a response of CR, a full assessment of all target and nontarget lesions that were present at baseline must occur, including those measured by bone scan. To confirm a PR or SD, a full assessment of target lesions that were present at baseline must occur; assessment of nontargets is not required.

However, in *randomized trial* (Phase 2 or 3) or studies where SD or progression is the primary endpoints, confirmation of response is not required. But, elimination of the requirement may increase the importance of central review to protect against bias, in particular of studies which are not blinded.

In the case of SD, follow-up measurements must have met the SD criteria at least once after start of treatment at a minimum interval not less than 6 weeks measured from first dose.

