### **10.3. Efficacy Evaluations**

A secondary objective of the study is to document any antitumor activity. Refer to [Attachment 1](#) for details regarding the timing of specific efficacy measures. Efficacy measures include:

- ORR: The proportion of patients who exhibit a confirmed complete response (CR) or PR relative to baseline as defined by RECIST 1.1 (Eisenhauer et al. 2009)
- DCR: The proportion of patients in the analysis population who exhibit a SD or confirmed CR or PR relative to baseline during the study
- PFS: The time from the date of study enrollment to the date of first observation of objective progression or death from any cause
- Change in tumor size: The change in tumor size from baseline measurement to the measurement with the smallest tumor size during the study.

Each patient will be assessed by one or more of the following radiologic tests for tumor measurement:

- CT scan
- MRI
- Chest x-ray.

Each patient's full extent of disease will also be assessed with:

- Tumor measurement by RECIST 1.1 (Eisenhauer et al. 2009)
- Evaluation of tumor markers, if indicated
- Evaluation of ECOG performance status (refer to [Attachment 6](#)).

Consistent with RECIST, all patients may undergo alternative imaging studies consistent with institutional guidelines to assess tumor response. This may include, but is not limited to, FDG-PET, dynamic contrasted-enhanced MRI, or other modalities.

To confirm objective responses, all lesions should be radiologically assessed, and the same radiologic method used for the initial response determination should be repeated at least 4 weeks following the initial observation of an objective response, using the sample method that was used at baseline. If a patient is discontinued from the study, repeat radiology assessments may be omitted if clear clinical signs of progressive disease are present.

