Radiological Tumor Assessment g	X										Every 6 weeks after initiation of study treatment; after Cycle 9 every 2-4 cycles as clinically indicated	
Functional Tumor Imaging	X h										FDG-PET mandatory in Part B1 (gastric) 6 weeks after initiation of study therapy	

Abbreviations: CNS = central nervous system; CT = computed tomography; CTCAE = Common Terminology Criteria for Adverse Events; DCE-MRI = dynamic contrasted-enhanced magnetic resonance imaging; ECG = electrocardiogram; ECOG = Eastern Cooperative Oncology Group; FDG-PET = 2-deoxy-2[F-18]fluoro-D-glucose positron emission tomography; FLT-PET = 3-deoxy-3[F-18]fluorothymidine positron emission tomography; fT4 = free thyroxine; PD = pharmacodynamics; PET = positron emission tomography; PK = pharmacokinetics; TSH = thyroid-stimulating hormone; V = visit.

a Short-term follow-up begins on the day after the patient's last dose of study drug and ends approximately 30 days later. This visit should be scheduled  $30 \pm 3$  days after last dose of study drug.

b Electrocardiograms must be recorded before any study drug is administered. In Cycle 1, Day 1 and 15 only, additional ECGs must be recorded pre- and post-LY2875358 infusion, immediately before collecting the corresponding PK samples.

- c Local hematology, coagulation tests, and urinalysis may be done within 2 days prior to administration of study drugs (except Cycle 1, Day 1 [within 3 days]). An additional local chemistry panel according to local standard of care may be done and used for on-study dosing decisions; if done so, chemistry testing must also still be performed by the central laboratory at the regularly scheduled time points. The central chemistry laboratory results will be used for patient eligibility and subsequent safety analyses. In exceptional cases, patient may be enrolled based on local chemistry results after discussion with the sponsor if central laboratory samples results required for eligibility are not available in a timely manner (e.g., due to inclement weather conditions).
- d If, while receiving the investigational product(s), a patient has proteinuria  $\geq 2+$  per a dipstick or routine urinalysis test, a 24-hour urine collection will be conducted prior to the subsequent scheduled treatment (see Section 9.2.3.2.2).
- e Samples will be collected at Cycle 3, Cycle 5, Cycle 7, Cycle 9, and every 4 cycles thereafter while patient is on study treatment.

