- f If a patient experiences an infusion-related reaction (see Section 9.2.3.1), immunogenicity samples for anti-ramucirumab and anti-LY2875358 antibodies and PK samples will be taken as close to the onset of the event as possible, at the resolution of the event, and approximately 30 days following the event.
- g The method of assessment used at baseline must be used consistently for tumor assessment and will be repeated approximately every 6 weeks ( $\pm 7$  days) during the study treatment period for lesions outside the CNS. For those patients with known CNS metastases, ongoing CNS surveillance using the same modality is required approximately every 12 weeks ( $\pm 7$  days). Positron emission tomography /CT is allowed if CT portion is of diagnostic quality.
- h For patients in Part B1 (gastric), the mandatory FDG-PET approximately 6 weeks ( $\pm 7$  days) after initiation of study treatment should be performed only if the baseline FDG-PET demonstrated PET avid lesion(s). Further functional tumor imaging (including but not limited to DCE-MRI, FLT-PET) is permitted throughout the study in all patients if appropriate for the respective tumor type at the discretion of the investigator and considered as institutional standard of care or is part of an appropriate imaging study open at the site.

---

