## Attachment 8. Protocol JTBF RECIST Criteria 1.1

---

Response and progression will be evaluated in this study using the international criteria proposed by the New Response Evaluation Criteria in Solid Tumors (RECIST): Revised RECIST Guideline (version 1.1; Eisenhauer et al. 2009).

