Death or progression after more than one missed visit (after 3 months since last assessment)	Censored	Date of last radiologic assessment of measured lesions showing no progression prior to the missed visit

The date of first documented objective disease progression must be recorded on the CRF even if it occurs after the patient has started a new therapy.

Disease Control Rate (DCR): The proportion of patients in the analysis population who exhibit an SD or confirmed CR or PR relative to baseline during the study. Response is defined by RECIST 1.1 (Eisenhauer et al. 2009).

Change in Tumor Size (CTS): The change in tumor size from baseline to the measurement with the smallest tumor size during the study period. Change in tumor size will be assessed in each patient using radiographic imaging. The tumor size of target lesions will be determined as defined by RECIST 1.1 (Eisenhauer et al. 2009).

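### Stable disease must be seen at least 42 days after first dose, but the first scan is in window from day 35, so some on-time scans cannot qualify and DCR can be lowered

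*Protocol*

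**What the plan says.** Protocol Attachment 8 is the response standard for the trial: "Response and progression will be evaluated in this study using the international criteria proposed by the New Response Evaluation Criteria in Solid Tumors". Under its heading on confirmation and duration of response, it requires for SD that "follow-up measurements must have met the SD criteria at least once after start of treatment at a minimum interval not less than 6 weeks", counted from first dose.

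The study schedule (protocol Attachment 1) sets radiological assessment as "Every 6 weeks after initiation of study treatment; after Cycle 9 every 2-4 cycles as clinically indicated". Its footnote g says that assessment "will be repeated approximately every 6 weeks", with a tolerance of 7 days either way, "during the study treatment period for lesions outside the CNS".

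DCR is defined in protocol Section 10.3 as "The proportion of patients in the analysis population who exhibit a SD or confirmed CR or PR relative to baseline during the study". SAP Section 6.12 uses almost the same words and refers response to RECIST 1.1. Neither definition repeats a minimum time for SD, gives the SD rule a scan-window tolerance, or says how SD seen before 6 weeks is classed when no later scan qualifies. Attachment 8 derives best overall response by an algorithm that is not set out. SAP Section 6.6 puts all treated patients in the efficacy population.

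**The concern.** The nominal time of the first scan equals the SD minimum exactly, so the early half of the scan's tolerance lies below that minimum. A site can keep to the schedule and still produce an assessment that cannot count.

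Take two patients with the same course: stable at the first scan and progressed by the second. One is scanned on day 38, the other on day 43. Under Attachment 8 the second has SD as best response and the first does not. The first stays in the denominator as a failure of disease control. Whether the algorithm labels that patient as progressive disease or as not evaluable is not stated, but neither label counts towards DCR.

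Early scans are plausible. Cycle 2 Day 15 is 28 + 14 = 42 days after first dose, so a scan booked shortly before that dosing visit falls on the wrong side. That is an inference about booking habits, because the documents give no distribution of scan times.

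At stake is the accuracy of a named efficacy measure and of the best-response table. Two analysts could also report different DCRs from the same data.

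**Working it through.** The plan states no target, power or sample size for DCR, so there is no figure of its own to reproduce. Days below are elapsed days from first dose.

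**Step 1: dates.** First-scan window = 42 ± 7 = days 35 to 49, which is 15 possible days. SD minimum = day 42. In-window days that cannot qualify: 35 to 41, which is 7 of 15. The second scan is due at 84 ± 7 = days 77 to 91. SD at that scan meets the rule, so only patients without a later qualifying scan are affected.

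**Step 2: who is lost.** The relevant patients are progression-free at day 42 but have progressed or died by about day 84. Loss in DCR = f × [S(42) − S(84)], where f is the share of first scans taken before day 42.

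**Step 3: inputs.** Median PFS is 2.1 months (gastric, protocol Section 5.2.1.1), 4.0 (HCC, Section 5.2.1.2), 7.1 (RCC, Section 5.2.1.3) and 3 (NSCLC, SAP Table JTBF.5.3). These are reference populations, not the combination. Assumed: exponential PFS, S(t) = 0.5^(t/median), with 30.4375 days per month. Also assumed: f, which may lie anywhere from 0 to 100%. I show 10%, 7/15 (scans spread evenly over the window) and 100%.

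| Cohort | S(42) | S(84) | Difference | f = 10% | f = 7/15 | f = 100% |
|---|---|---|---|---|---|---|
| Gastric/GEJ | 0.634 | 0.402 | 0.232 | 2.3 points | 10.8 points | 23.2 points |
| NSCLC | 0.727 | 0.529 | 0.198 | 2.0 | 9.3 | 19.8 |
| HCC | 0.787 | 0.620 | 0.167 | 1.7 | 7.8 | 16.7 |
| RCC | 0.874 | 0.764 | 0.110 | 1.1 | 5.1 | 11.0 |

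At f = 7/15, a cohort of 15 loses 15 × 0.051 ≈ 0.8 patients (RCC) to 15 × 0.108 ≈ 1.6 patients (gastric).

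**Step 4: check against the documents.** The gastric model gives 40.2% progression-free at 84 days, against the stated 12-week PFS of 40.1%. That supports the model at week 12 only. SAP Table JTBF.5.3 lists the gastric DCR as 49%. The gap between disease control and 12-week PFS is then 49 − 40.1 = 8.9 points, well below the modelled 23.2. At f = 7/15 the loss is 8.9 × 7/15 ≈ 4.2 points. This is indicative only, because the documents do not give that trial's SD minimum or scan window. For RCC the model gives 76.4% at 84 days, against a reported 12-week DCR of 64.1%, so it appears optimistic there as well.

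**The case against.** The strongest reply is that the DCR definitions in protocol Section 10.3 and SAP Section 6.12 set no SD minimum. On that reading SD at day 38 counts, and nothing is lost. The bias arises only if the best-response algorithm applies Attachment 8 strictly, which the documents do not spell out. This stands as a limit on certainty. It does not remove the point, because Attachment 8 governs response in this study and SAP 6.12 defers to RECIST 1.1. The two readings give different DCRs, and nothing in the text chooses between them.

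The second reply is that little depends on DCR. This stands in full. A reader might infer that go/no-go decisions are exposed, but the documents do not support that. The co-primary endpoint is ORR, which the SD minimum does not touch. The disease-control route to expansion (protocol Table JTBF.2) uses landmark PFS. The analyses are descriptive.

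A reader might also infer that the combination would look worse than the monotherapy DCRs in SAP Table JTBF.5.3 for scheduling reasons alone. That does not follow. The RCC figure of 64% is a 12-week DCR, and patients stable at the week-12 scan qualify anyway. For the gastric 49%, the SD minimum and scan window used are not given, so no scheduling disadvantage can be shown.

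Finally, it is tempting to start the at-risk interval before week 6. Starting at day 38 raises the gastric share from 23.2 to 26.0 points. The extra patients progress before 6 weeks and would not meet a 6-week standard on any schedule, so losing them is not understatement.

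**Conclusion.** The mismatch is certain: 7 of the 15 in-window days for the first scan cannot yield a qualifying SD, and no tolerance is stated. If Attachment 8 is applied as written, the effect runs one way, towards a lower DCR and a worse best overall response.

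The size is not certain. It rests on an assumed share of early scans, with a lower bound of zero, and on an exponential model that the documents' gastric figures suggest is too pessimistic about the loss. A fair statement is about 1 to 2 points if 10% of first scans are early and about 5 to 11 points if 7 in 15 are (roughly 1 to 2 patients per 15), with about 4 points for gastric at 7 in 15 from the documents' own numbers.

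The consequence is confined to a secondary, descriptive measure. It should still be corrected, because the rule misclassifies patients who were assessed on schedule and the correction is cheap.

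**What to change.** Choose one of two changes.

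1. In SAP Section 6.12 and Attachment 8, align the SD minimum with the scan window: SD criteria met at least once 35 or more days after first dose (6 weeks minus the 7-day window). State how SD seen earlier than that, with no later qualifying scan, is classed. Write the limit in elapsed days. Under the numbering in SAP Table JTBF.6.1, 35 elapsed days is Study Day 36.
2. In footnote g, make the window for the first scan 6 weeks −0/+7 days and leave the SD minimum at 6 weeks.

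Neither needs extra scans or patients. The first credits SD up to a week earlier, so a few patients who progress between days 35 and 42 could count as disease control. For example, a patient who progresses on day 40 would count if scanned on day 36 but not if scanned on day 45. The second avoids this at the cost of a narrower scheduling window, and it helps only patients whose first scan is still to come. Whichever is chosen, the best-response algorithm should state the same rule.

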#### *Duration of Overall Response*

The duration of overall response is measured from the time measurement criteria are first met for CR or PR (whichever is first recorded) until the first date that disease is recurrent or objective progression is observed (taking as reference for PD the smallest measurements recorded on study).

The duration of overall CR is measured from the time measurement criteria are first met for CR until the first date that recurrent disease is objectively documented.

*Duration of Stable Disease*

Stable disease is measured from the start of the treatment (in randomized trials, from date of randomization) until the criteria for objective progression are met, taking as reference the smallest sum on study (if the baseline sum is the smallest, that is the reference for calculation of PD).

**Independent Review of Response and Progression**

When objective response (CR + PR) is the primary end point, and when key drug development decisions are based on the observation of a minimum number of responders, it is recommended that all claimed responses be reviewed by an expert(s) independent of the study. If the study is a randomized trial, ideally reviewers should be blinded to treatment assignment.

---

**Attachment 9. Protocol Amendment I4C-MC-JTBF(b)  
Summary: A Phase 1b/2 Study of Ramucirumab in  
Combination with LY2875358 in Patients with Advanced  
Cancer**

---

## Overview

The overall changes and rationale for the changes made to this protocol are as follows:

- The primary rationale for amendment (b) is to is to modify Exclusion Criterion [28] and allow patients that have been previously treated with ramucirumab may be included in Part B1.
- Updated Sections 5.2.1 and 5.2.1.2 (ramucirumab clinical information)
- Updated Section 5.2.2 (LY2875358 clinical information)
- Modified Section 9.2.3 (dosage adjustments and delays) to align with discontinuation criteria
- Clarified Section 9.5 (use of granulocyte colony stimulating factor)
- Corrected Section 12.1 (approximately 70 patients may be enrolled in this multicenter Phase 1b/2 study)
- Minor editorial changes have been made throughout the protocol to improve clarity and practicability of the protocol.

## Revised Protocol Sections

**Note:** All deletions have been identified by ~~strikethroughs~~.  
All additions have been identified by the use of underscore.

### 5.2.1. Ramucirumab

Ramucirumab has been studied and/or continues to be investigated in ongoing clinical studies for multiple tumor indications. As of 31 December 2012, safety information was available for 1199 patients receiving ramucirumab in 7 Phase 1/1b studies, 16 open-label Phase 2 studies, and 1 Phase 3 study, including monotherapy and combination therapy with cytotoxic chemotherapy agents. In these studies, ramucirumab has demonstrated a favorable safety and clinical activity profile. The most frequently observed possibly related treatment emergent adverse events (TEAEs) of special interest include adverse events (AEs) which have been associated with anti-angiogenic agents and therapeutic mAbs, and include the following categories: infusion-related reaction, hypertension, proteinuria, arterial thromboembolic events (ATEs), venous thromboembolic events (VTEs), bleeding/hemorrhagic events, gastrointestinal (GI) perforation, impaired wound healing, reversible posterior leukoencephalopathy syndrome (RPLS), and congestive heart failure (CHF) in patients who received ramucirumab following prior anthracycline therapy.

Data from Phase 1, 2, and 3 studies provide supporting evidence for ramucirumab activity in advanced solid tumors, including gastric or GEJ adenocarcinoma, hepatocellular carcinoma, renal cell cancer, and NSCLC.

The results of these preclinical pharmacodynamic studies supported the initial investigation of ramucirumab in the treatment of solid tumors.

Clinical investigations with ramucirumab in solid tumors have resulted in 4 positive Phase 3 trials, with 2 in gastric cancer (REGARD and RAINBOW), 1 in NSCLC (REVEL), and 1 in metastatic colorectal cancer (CRC; RAISE). Ramucirumab (Cyramza®) is approved in the United States as a single agent or in combination with paclitaxel as a treatment for people with advanced or metastatic gastric or gastroesophageal junction adenocarcinoma whose cancer has progressed on or after prior fluoropyrimidine- or platinum-containing chemotherapy, and in combination with docetaxel as a treatment for people with metastatic NSCLC whose cancer has progressed on or after platinum-based chemotherapy. In addition, the European Commission approved ramucirumab (Cyramza) in combination with paclitaxel and as a single agent when combination therapy is not appropriate, for people with advanced gastric cancer after prior chemotherapy.

More information about the known and expected benefits, risks, and reasonably anticipated adverse events (AEs) of ramucirumab may be found in the IB. Information on AEs expected to be related to ramucirumab may be found in Section 7 (Development Core Safety Information [DCSI]) of the IB. Information on serious adverse events (SAEs) expected in the study

population independent of drug exposure and that will be assessed by the sponsor in aggregate, periodically during the course of the study, may be found in Section 6 (Effects in Humans) of the IB.

### **5.2.1.2 Ramucirumab and Hepatocellular Cancer**

A randomized, controlled Phase 3 trial of ramucirumab monotherapy versus placebo in a second-line setting (post-sorafenib) for advanced hepatocellular carcinoma is currently ongoing (NCT01140347).

A randomized, controlled Phase 3 trial (Study I4T-IE-JVBF; Study JVBF, also known as REACH) of ramucirumab monotherapy versus placebo in a second-line setting (post-sorafenib) for advanced HCC is currently ongoing (NCT01140347). Study JVBF is a global, randomized, double-blind Phase 3 study of ramucirumab plus BSC compared to placebo and BSC as a second-line treatment in patients with HCC who have been previously treated with sorafenib in the first-line setting. The study did not meet its primary endpoint of OS; although the OS results favored the ramucirumab arm, they were not statistically significant. Encouraging single-agent ramucirumab activity was observed, with meaningful improvements in key secondary endpoints of PFS, objective response rate (ORR), and time to progression (TTP).

